Sponsor	The University of Liverpool is the research Sponsor for this Study. It is recognised that as an employee of the University the Chief Investigator has been delegated specific duties, as detailed in the Sponsorship Approval letter. For further information regarding the sponsorship conditions, please contact: [name] Senior Clinical Research Governance Manager

	[contact]
Key Protocol Contributors	
[name] [contact]
 
[name] [contact]
 
[name] [contact]
 
[name] [contact]
 
[name] [contact]
 
[name] [contact]
 
[name] [contact]
 
[name] [contact]
 
[name] [contact]
 
[name] [contact]

Study Summary

Study Design	A randomised controlled feasibility study with nested qualitative study
Study Participants	People with multiple sclerosis
Planned Size of Sample (if applicable)	68
Follow up duration (if applicable)	6 months
Planned Study Period	30 months 1 st April 2025 to 30 th September 2027
Research Question/Aim(s)	
Study aim
 
To determine the feasibility and acceptability of SNMES as an exercise therapy, for preventing muscle weakness, improving walking, fatigue and quality of life in people with MS to inform a future definitive trial of clinical and cost effectiveness.
 
Study objectives:
 
 • Estimate screening, recruitment and attrition rates. • Determine the acceptability of the intervention and key aspects of study design including intervention • adherence rates, drawing on the Theoretical Framework of Acceptability (TFA) • Explore, via qualitative interviews, individuals' experiences of study participation (and where possible, reasons for non-participation) to gather feedback about the intervention, outcome measures and study procedures. • Inform primary outcome measure selection for a future trial. • Determine sample size for a future trial, informed by parameter estimates of outcomes. • Evaluate the acceptability and feasibility of health economics measures, including selection and ordering of questionnaires.

Funding and Support in Kind

FUNDER(S)	FINANCIAL AND NON-FINANCIAL SUPPORT GIVEN
NIHR - Research for Patient Benefit (RfPB) Programme: NIHR207134	£245,096.00

Protocol Contributors

The Chief Investigator and all co-investigators have contributed to the development of the protocol.

[figure not shown]
PPIE has contributed to the development of study materials and processes that are referenced in this document.

[figure not shown]

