7.4 STUDY DESIGN AND METHODS OF DATA COLLECTION

7.4.1 Study design

A randomised controlled feasibility study comparing SNMES plus usual care versus usual care only with a nested qualitative study.

This will involve

- 1) A randomised controlled trial comparing SNMES plus usual care (n=25) versus usual care only (n=25). Total of 50 participants.
- 2) A nested qualitative study using semi-structured interviews for people with MS who took part in either arm of the randomised controlled trial and their carers (n=15-20).
- 3) A nested qualitative study using semi-structured interviews for healthcare practitioners and staff who were involved in the set up or delivery of the study and intervention (n=6-8).

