9 STATISTICS AND DATA ANALYSIS

9.1 SAMPLING

9.1.1 Sample Size

Quantitative sample size

As this is a feasibility study, no formal sample size calculation for comparative estimates has been carried out. The aims are to provide robust estimates of rates of consent, retention, and adherence to the intervention and to gain estimates of the outcome event rates to accurately inform power calculations for a future definitive trial. We aim to recruit 50 participants across two sites over a 15-month period. Allowing for 20% loss to follow up, data will be available for 40 participants. A sample size has been chosen to ensure the objectives of the study can be met.

If we identify 100 eligible patients, we will be able to estimate a consent rate of 50% to within a confidence interval of +/-10%. If 50 patients are recruited, we will be able to estimate a retention rate of 80% to within a confidence interval of +/-11%. If we obtain complete data on 40 participants, we will be able to estimate an adherence rate of 60% to within a confidence interval of +/-15%.

Nested qualitative study

We will conduct semi-structured interviews with people with MS and their carers (n=15-20), and separate interviews with clinicians (n=6-8) who supervised/delivered the intervention. Sample size is informed by the information power concept, taking account of the study's well-defined aim, focused data gathering, preparation and ongoing review to enable informative dialogue during interviews and use of case analysis in combination with previous research.⁷⁵

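### The Study Summary plans a sample of 68 beside a row naming only people with MS, but sections 7.4.1 and 9.1.1 plan 50, and 68 is never explained

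*Protocol*

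**What the plan says.** The Protocol gives its planned size in three places.

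- **Study Summary.** The row "Planned Size of Sample (if applicable" holds 68. The row for study participants reads "People with multiple sclerosis" and mentions neither carers nor staff.
- **Section 7.4.1 (Study design).** "A randomised controlled trial comparing SNMES plus usual care (n=25) versus usual care only (n=25). Total of 50 participants". The same list then adds interviews with 15–20 people with MS and carers taken together, and with 6–8 practitioners and staff.
- **Section 9.1.1 (Sample Size).** "We aim to recruit 50 participants across two sites over a 15-month period", followed by "Allowing for 20% loss to follow up, data will be available for 40 participants".

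Section 9.1.1 states precision for consent, retention and adherence, each with its own denominator (100 eligible, 50 recruited, 40 with complete data). The figure 68 does not appear there, in section 7.4.1, or in the progression criteria in section 9.2.1.

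**The concern.** The planned sample size is a headline figure, and the summary is where many readers look for it first. Read as laid out, the summary plans 68 people with MS, 18 more than the two sections that set the design and justify the size.

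Estimating recruitment is part of the first objective in section 5.1. Whoever reports accrual needs one target to report against, and the Protocol supplies two with no statement of how they relate. The pace each implies also differs, if 68 is read as the number to randomise in the same 15 months.

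**Working it through.** **Inputs.** 68 (Study Summary); 25 + 25 = 50 (section 7.4.1); 50 recruited at two sites in 15 months, 20% loss, 40 with data (section 9.1.1); interviews with 15–20 people with MS and carers combined and with 6–8 staff (sections 7.4.1 and 9.1.1). The confidence level is not stated. I assume two-sided 95%, which reproduces the stated figures.

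**Step 1. Which size do the stated precision figures use?** Half-width = 1.96 × √(p(1 − p)/n).

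| Rate | p | n | Computed | Stated |
|---|---|---|---|---|
| Consent | 0.50 | 100 | 1.96 × √(0.25/100) = 9.8% | ±10% |
| Retention | 0.80 | 50 | 1.96 × √(0.16/50) = 11.1% | ±11% |
| Adherence | 0.60 | 40 | 1.96 × √(0.24/40) = 15.2% | ±15% |

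The attrition step also closes: 50 × 0.80 = 40. All the figures reproduce, and all belong to the plan for 50.

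**Step 2. Is 68 an inflated 50?**

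- Dividing by the retained fraction: 50/0.80 = 62.5, rounded up to 63.
- Multiplying by 1.2: 50 × 1.2 = 60.
- In the other direction: 68 × 0.80 = 54.4, so about 54 with data. Section 9.1.1 says 40, and 54 appears nowhere.

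Loss to follow-up does not explain 68.

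**Step 3. Is 68 a head-count of the whole study?** Interviewed people with MS come from the randomised trial (sections 7.1.3 and 7.4.1), so they are already among the 50. Only carers and staff are additional:

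head-count = 50 + carers + staff, so 68 requires carers + staff = 18.

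With 6–8 staff, this is met by 10 carers + 8 staff, 11 + 7, or 12 + 6. Each carer number fits inside the 15–20 interviews. The Protocol does not divide those 15–20 between people with MS and carers, so none of the three splits can be confirmed.

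**Step 4. What difference does the choice of target make?**

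- Share of plan if 50 are recruited: 50/50 = 100%, or 50/68 = 73.5%, about 74%.
- Pace over 15 months at two sites: 50/(15 × 2) = 1.67 per site-month, or 68/(15 × 2) = 2.27.

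**The case against.** The best defence is that 68 is a whole-study total with its label missing. The design row of the same summary table includes the nested qualitative study, so a total across all groups is a natural entry. Section 7.2.2 recruits people with MS and carers as dyads but interviews them separately; 20 interviews as 10 dyads would give 10 carers, and with 8 staff the sum is exactly 68. On that reading there is a single trial target of 50 and no statistical consequence.

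Much of this stands. The reading is plausible, and the two operative sections do agree on 50. It does not rescue the entry as written: the sum is nowhere shown, and the participant row names only people with MS, whom 18 of the 68 would not be.

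A reader might try to rule out the head-count by adding every interview to the trial: 50 + 15 + 6 = 71 up to 50 + 20 + 8 = 78, a range that excludes 68. That sum counts the interviewed people with MS twice and should not be used.

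A reader might also infer that the precision figures rest on two different sizes. Step 1 shows that they do not. Nor do the documents show that 68 was carried into an ethics application, a registry entry or accrual reports; it may have been, but that would have to be checked.

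**Conclusion.** The contradiction is real and should be corrected: 68 in the summary, apparently of people with MS, against 50 in sections 7.4.1 and 9.1.1, with no derivation or label for 68. The Protocol's text does not settle whether 68 is a wrong number or an unlabelled head-count. Either way the summary row needs changing.

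The effect is confined to the stated target: a gap of 18 people, and 74% or 100% of plan for the same 50 recruits. It does not reach the precision statements, which are internally consistent at 50. It does not reach the progression criteria in section 9.2.1 either, which use the consent rate among eligible people, retention at 6 months and session counts, with no recruitment total. No analysis or design feature is invalidated. The 74% assumes that a reader takes the summary's 68 at face value as the number of people with MS to recruit.

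**What to change.** In the Study Summary, state 50 people with MS randomised, 25 per arm. Below it, give carers to be interviewed and staff to be interviewed (6–8) on separate lines, each with its own number. Because section 9.1.1 gives only a combined 15–20 for people with MS and carers, the planned number of carers has to be written down for this. State as well that the interviewed people with MS are drawn from the 50.

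If 68 is meant as a total head-count, keep it, label it as the total across people with MS, carers and staff, and show the sum.

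The cost is a few lines of wording in the summary, plus a check whether 68 was copied into other study documents. Design, sample-size reasoning and analysis do not change.

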1 INTRODUCTION

This protocol describes a randomised controlled feasibility study investigating surface neuromuscular STIMulation as an exercise therapy versus usual care in people with multiple sclerosis (MS) to help improve lower limb strength, walking and fatigue (STIM-MS) and provides information about procedures for entering participants, study procedures, safety reporting and governance requirements. Every care was taken in its drafting, but corrections or amendments may be necessary. These will be circulated to investigators in the study following receipt of required approvals.

Queries relating to this Study should be referred, in the first instance, to [name]. This study will adhere to the principles outlined in the UK Policy Framework for Health and Social Care Research. It will be conducted in compliance with the protocol, the Data Protection Act 2018 and the UK GDPR as amended from time to time and any successor legislation in the UK and any other directly applicable regulation relating to data protection and privacy as well as any other regulatory requirements as appropriate.

2 BACKGROUND

Maintaining the ability to walk is the most important thing to people with MS.¹ Nearly half of all people with MS report difficulties with mobility one month after receiving a formal diagnosis.^{2,3} At 10-years, 25% to 60% of people with MS are unable to walk without walking aids and 8% to 20% will be restricted to using a wheelchair or bed.⁴ Walking ability is strongly linked to physical activity levels, long term management and ability to cope with MS, self-efficacy, employment status, care needs, fall risks and quality of life.³ The annual economic impact of MS is approximately £1.4 billion.⁵ Direct and indirect medical costs are 2 to 4 times higher in those with affected levels of mobility (<£1,000/person vs £2,000 to £4,000/person).⁵

Changes in walking ability, which correspond to Expanded Disability Status Scale (EDSS) categories, are associated with increased healthcare costs.⁵⁻⁷ The EDSS score is a way of measuring how much someone is affected by MS and looks mainly at walking ability and other body functions such as muscle weakness, balance, tremors, eye movements and vision, swallowing, speech, sensory changes, bladder and bowel control, cognition, and memory. As people move from being independently mobile with no restrictions (EDSS 0 to ≤4) to needing

walking aids and having limited mobility (EDSS groups >4 to ≤7.5) mean costs in € (purchasing power parity (PPP)) increase from approximately €22,800 to €37,100 respectively. Once people become restricted to a bed or wheelchair (EDSS groups ≥8), care costs further increase to €57,500.⁷ Worsening mobility and EDSS scores are associated with increased non-medical costs related to hospital attendances (inpatient, outpatient and emergency department), rehabilitation at home, aids and orthotics, modifications to people's homes and indirect costs to both people with MS and their caregivers.⁶

There are limited exercise-based rehabilitation options for people with MS and mobility issues (EDSS ≤4), particularly those with more progressive or higher levels of disability.⁸⁻¹⁰ Current "usual" therapies have limited value as most people with MS are unable to participate at the required exercise intensity levels for improving or maintaining leg strength for walking¹¹ and achieving secondary health benefits. This may be due to severe fatigue, pain, spasms, low mood and depression, cognition, heat sensitivity, restricted joint movements (limb deformities) and spasticity.^{12,13}

2.1 HOW DOES THE EXISTING LITERATURE SUPPORT THIS PROJECT?

Active exercise for MS is the primary method to prevent deterioration in both muscle structure and function (strength and fatigue).^{9,10,14} However, people with MS who struggle to walk independently or without walking aids, may be unlikely to engage in exercise at an intensity that prevents progressive muscle wasting and deterioration in function. This could explain the small effect sizes associated with traditional exercise treatments.¹⁴

There are no phase III studies investigating the use of SNMES in people with MS.¹⁵ Preliminary studies suggest that it can preserve or improve muscle structure and function, fatigue and potentially increase engagement with exercise-based interventions. However, existing studies are limited by small sample sizes and high drop-out rates.¹⁶⁻²⁰ Several studies have evaluated the broader use of electrical stimulation in MS; however, these have focused on functional electrical stimulation (FES) or assisted cycling, which are used in a distinctively different way to SNMES. FES can address impairments in walking, at a single joint e.g. lifting the foot up, but is not effective for strengthening and slowing down progressive changes in the lower-limb.²¹ Cycling with electrical stimulation may increase leg strength and cardiovascular fitness but is not practical for all people with MS and settings, as it requires specialist and expensive equipment.^{17,19}

2.2 EVIDENCE FOR SNMES IN DIFFERENT CLINICAL POPULATIONS

SNMES can help people whose conditions or symptoms prevent them engaging with conventional exercises at the required intensity for improving muscle strength and function. SNMES has been used to increase muscle strength and function in healthy individuals²² and in multiple clinical conditions including stroke,^{23,24} chronic obstructive pulmonary disease,^{25,26} advanced coronary heart disease, thoracic cancer, older adults,²⁷ musculoskeletal and orthopaedic injuries,²² dysphagia,²⁸ urinary incontinence²⁹ and hospitalised adults in ICU and non-ICU settings.³⁰ However, the majority of reviews conclude that the overall quality of evidence in support of SNMES is low-quality and further research of higher methodological quality is needed.

A 2023 systematic review concluded that SNMES combined with exercise significantly increases lower-limb muscle strength and power in both healthy individuals and those with musculoskeletal and orthopaedic injuries.²² A 2018 Cochrane review in chronic obstructive pulmonary disease identified low quality evidence that SNMES in isolation increased muscle force, endurance, and walking performance (distance walked in 6-minutes) and time to symptom onset whilst decreasing reported leg fatigue.²⁵ When combined with exercise, SNMES increased walking performance and reduced time confined to a hospital bed (5 days) but evidence was low or very low quality. Evidence for combined SNMES and exercise on muscle force and quadriceps endurance was uncertain and of very low quality.²⁵ A more recent 2022 systematic review, based on similar studies identified low and very low quality evidence that SNMES increases exercise capacity and muscle strength in chronic obstructive pulmonary disease.²⁶ A 2016 Cochrane review reported SNMES improved quadriceps strength, muscle mass, and walking performance in advanced diseases including coronary heart disease, thoracic cancers and chronic obstructive pulmonary disease, although evidence was low quality.¹⁵ A 2023 systematic review identified that SNMES improved walking performance in non-ICU hospital patients and muscle strength in ICU and non-ICU settings hospital settings.³⁰ A 2017 systematic review identified improvements in leg strength and balance in the older adults using SNMES.²⁷

SNMES for the upper limb has been shown to have a moderate effect on functional activities of daily living, with only a trend observed in the lower-limb.²³ However, there are limited studies investigating use of SNMES in the lower-limb for stroke.²³ SNMES is recommended for strengthening muscles required for function in current clinical stroke guidelines for upper-limb

rehabilitation²⁴ and NICE guidelines for adults with dysphagia²⁸ and stress urinary incontinence.²⁹

2.3 PREVIOUS PILOT WORK

We have demonstrated that SNMES is acceptable to and feasible for unimpaired and older adults.³¹ Preliminary results suggest SNMES may increase lower-limb strength and muscle hypertrophy, particularly in those who have a previous history of exercising.³¹ Our upper limb neurorehabilitation SNMES research in people affected by stroke has shown it to be acceptable and feasible,³² with an evaluation in patients and therapists of barriers and facilitators to its use, which have been used to inform this study.³³ We have conducted phase I and II randomised controlled trials investigating if upper limb SNMES can be used to prevent complications (pain and contractures) associated with disuse in stroke survivors.³⁴⁻³⁷ Disuse in both stroke and MS causes muscle wasting and decreased strength which is reversible with SNMES. Prolonged disuse can cause irreversible changes to the muscle resulting in contractures and limb deformities, which limits exercise ability and subsequent treatment effectiveness. SNMES may prevent these occurring.

3 RATIONALE FOR CURRENT STUDY

Mobility loss is considered one of the most disabling and visible consequence of MS.³⁸ This application addresses five priorities for MS from the James Lind Alliance i.e. evaluating which treatments are effective to slow, stop or reverse the accumulation of disability (priority-1), help fatigue (priority-3), support self-management (priority-4), improve mobility (priority-7) and evaluate physiotherapy's effectiveness in reducing disability (priority-10).³⁹

SNMES has been used to make the muscles of people with MS contract in a similar way to resistance training, achieving the levels required to preserve or improve muscle structure and function needed to help with mobility and walking.¹⁶⁻²⁰ SNMES could address existing barriers to exercise experienced by people with MS, such as access to exercise facilities, expensive equipment and fatigue.^{40,41} This would enhance individuals' ability and opportunities (key components of the COM-B (Capability-Opportunity-Motivation-Behaviour) model), for engagement in exercise-based rehabilitation, potentially increasing independence and quality of life, whilst also decreasing years lost to disability.¹¹

If people with MS maintain or improve their leg strength this can keep them walking for longer and prevent a downward spiral of reduced exercise tolerance, progressive muscle wasting and leg weakness, worsening fatigue and sequelae associated with physical deconditioning e.g. joint contractures and cardiovascular complications. Ultimately this could reduce the care burden experienced by people with MS, their carers and the services used in the management of their condition.

4 THEORECTICAL FRAMEWORKS

This project will draw on several theoretical frameworks as identified below.

SNMES intervention

The delivery and rationale for the intervention is informed by the COM-B (Capability-Opportunity-Motivation-Behaviour) model (figure 1).¹¹ The SNMES intervention addresses components related to capability and opportunity. SNMES could address existing barriers to exercise experienced by people with MS, such as access to exercise facilities, expensive equipment and fatigue.^{40,41}

[figure not shown]

Figure 1. Outline of the COM-B model

Image taken from The decision lab - <https://thedecisionlab.com/reference-guide/organizational-behavior/the-com-b-model-for-behavior-change>

To facilitate engagement and compliance with the intervention, the following health behaviour strategies will be used in line with the COM-B model. During the intervention participants will

- Be provided with education of SNMES use and expectations. These will be delivered verbally and in accessible written and audio/ video formats. During the education sessions people will be instructed how to perform the behaviour and provide background information, discuss goal setting, problem solving and commitment.

- These will be supported by a resource provided to participants for goal setting alongside logging their use of the device, identifying aspects of their care and for facilitating compliance and retention.
- Undertake graded increments of SNMES use and intensity to facilitate a sense of achievement.
- Participants will be contacted after the first week and at 6-weeks to see how they are getting on (behavioural monitoring with feedback).
- Participants will also be provided with technical support contact details (social support practical).

Recruitment and retention

To facilitate recruitment and mitigate against drop out we will draw on behavioural interventions and a combined strategy approach (figure 2).⁴² This will be applicable to people involved in running the study and participants.

[figure not shown]

Figure 2. Overview of the behavioural strategy intervention to facilitate retention. Image taken from Coffey et al 2023 <https://doi.org/10.1186/s13063-023-07268-2>

Development of topic guides and analysis of study findings

The nested qualitative study will draw on the Theoretical Framework of Acceptability (TFA)⁴³ for development of the topic guides and mapping of the qualitative findings from the semi-structured interviews for participants and people involved in delivering the study (figure 3).

[figure not shown]

Figure 3. The theoretical framework of acceptability. Image taken from Sekhon et al 2022

<https://doi.org/10.1186/s12913-022-07577-3>

